5.2. SUBJECT EXCLUSION CRITERIA

An individual who meets any of the following criteria will be excluded from participation in this study:

- Presence of any other systemic or chronic pain disorder
- History or current evidence of a psychotic disorder (e.g. schizophrenia) or substance abuse; bipolar or severe major depression, as evidenced by Beck Depression score of ≥ 20*
- Prior use of tDCS
- Ongoing, unresolved disability litigation
- History of neurological disorder (e.g. epilepsy, stroke, neuropathy, neuropathic pain)
- Current use of opioid pain medications
- Allergic response to study radiotracers or chemically-related drugs
- Excluded by MRI Center or PET Center safety screening checklist (as administered by study staff)
- Female participants who are pregnant, nursing, or planning a pregnancy, or who are of childbearing potential and are not using a reliable means of contraception during the baseline and study periods (negative urine pregnancy test must be available before any procedures are initiated)
- Treatment with an investigational drug, device or other intervention within 30 days of study enrollment (Screening Visit).
- Anything that would place the individual at increased risk or preclude the individual's full compliance with or completion of the study (eg, medical condition, laboratory finding, physical exam finding, logistical complication).

^{*} The Beck Depression Inventory will be graded by study staff at the time of completion. Individuals with a score of ≥ 30 will be provided with a pamphlet from the Michigan Depression Center that contains information and contacts regarding depression. In addition, those individuals who respond to question #9 with answers #2 or #3, will be provided with a flyer from the Department of Health and Human Services National Suicide Prevention Lifeline (800 number and website).

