5.3. STRATEGIES FOR RECRUITMENT AND RETENTION

We will recruit 60 episodic migraine patients divided into 2 groups: 30 for the active M1 HD-tDCS group and 30 for the placebo HD-tDCS group. In addition, we will use the data from up to 10 healthy controls who were recruited and scanned during the NINDS-K23062946 project (IRBMED #HUM00027383; [name], Principal Investigator). We will then recruit healthy volunteers to a total of 30 age- and gender-matched healthy subjects.

Recruited patients will be screened from the UMClinicalStudies.org (formerly Engage) recruitment network and the University of Michigan. In addition to active referral from pain centers, advertisements will be placed in other pain clinics in the region. In-hospital advertisements will also be placed in pain clinics and departments at the institution, as well as across the university.

Subjects recruited will be prescreened by phone using an initial IRB-approved questionnaire. Those who pass the phone screening will be scheduled for an in-person Screening Visit, which will commence with a verbal and written informed consent process. Once informed consent has been obtained, subjects will undergo further screening by obtaining a history and performing a physical exam and QST. Those subjects who are determined to be eligible to enter the study will be enrolled into either the migraine or healthy volunteer pools; if migraine, they will be randomized to active or sham treatment.

Study duration per subject is expected to be less than 3 months; however due to the scheduling of PET and MRI visits, visit reminders (eg, phone and/or email; subject preference) may be implemented to help with retention.

During the course of participation, subjects will be compensated according to amounts stated in the informed consent form and approved by the IRB.

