5.5. REASONS FOR WITHDRAWAL

Subjects are free to withdraw from participation in the study at any time upon request.

An investigator may terminate a study subject's participation in the study if:

- Any clinical adverse event (AE), laboratory abnormality, or other medical condition or situation occurs such that continued participation in the study would not be in the best interest of the subject.
- The subject meets an exclusion criterion (either newly developed or not previously recognized) that precludes further study participation.

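### For a Beck item 9 answer of 2 or 3 the protocol prescribes only a lifeline flyer, with no step ensuring that an investigator considers the answer before eligibility is decided

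*Combined protocol and SAP*

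**What the plan says.** Section 5.2 lists the exclusions. Its opening line is mandatory: "An individual who meets any of the following criteria will be excluded from participation in this study". The depression criterion is "severe major depression, as evidenced by Beck Depression score of ≥ 20", which is a rule on the total score.

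The footnote to that criterion adds three things:

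- On timing: "The Beck Depression Inventory will be graded by study staff at the time of completion". Appendix A marks the Beck once, in the Screening column.
- A total of 30 or more leads to a pamphlet on depression.
- On item 9: "those individuals who respond to question #9 with answers #2 or #3, will be provided with a flyer". The flyer gives a national lifeline number and website.

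On the form in Appendix B, item 9 is the suicide item. Answer 2 states a wish to kill oneself. Answer 3 states that the person would do so given the chance.

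The last exclusion in 5.2 is a general one that begins "Anything that would place the individual at increased risk". Its examples are "eg, medical condition, laboratory finding, physical exam finding, logistical complication".

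Section 5.3 describes entry to the study: "Those subjects who are determined to be eligible to enter the study will be enrolled into either the migraine or healthy volunteer pools". It does not say who makes that determination.

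**The concern.** The protocol anticipates these two answers and writes a specific rule for them, and that rule ends with a leaflet. It does not ask the person grading the form to tell an investigator, and it does not hold eligibility until someone has considered the answer. The score criterion does not fill the gap, because item 9 contributes only 2 or 3 points to a total that must reach 20.

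This is a matter of participant safety. Staff can follow the footnote exactly and still let eligibility proceed without an investigator having weighed a stated wish or intent to die. For a migraine patient, eligibility leads to randomization, PET and MRI scans, and ten stimulation sessions. Section 9.1 names consent and screening as the study's safety parameters, so a gap at Screening matters more here than it would in a trial with other formal safety reviews.

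**Working it through.** The plan gives no figure to reproduce. The check has two parts: whether the score criterion catches these answers, and whether any other text does.

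**Score criterion**

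Inputs: the Beck form in Appendix B has 21 items, each scored 0 to 3; section 5.2 excludes at a total of 20 or more.

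- Highest total not excluded by score: 20 − 1 = 19.
- Maximum on the other 20 items: 20 × 3 = 60.
- Item 9 = 2: the other items may total up to 19 − 2 = 17, an average of 17/20 = 0.85 per item, or 17/60 = 28% of the available points.
- Item 9 = 3: the other items may total up to 19 − 3 = 16, an average of 16/20 = 0.80 per item, or 16/60 = 27% of the available points.

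So the score criterion does not guarantee exclusion for either answer. The pamphlet threshold adds nothing, because a total of 30 or more is already excluded.

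**Other text that might bring the answer to an investigator**

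| Place | What it provides | Does it ensure review before eligibility? |
|---|---|---|
| 5.2, last criterion | Mandatory exclusion if the person is judged to be at increased risk | No. Item 9 is not mentioned and no one is assigned to judge it |
| 5.3 | Eligibility is determined after history, physical exam and QST | No. No decision-maker is named and questionnaire answers are not mentioned |
| 5.4.1 | Randomization follows clinical exam and migraine diagnosis | No. The Beck is not mentioned |
| 5.5 | An investigator may terminate participation | No. It applies to people already in the study and depends on someone noticing |
| 9, opening paragraph | Grossly abnormal findings may be shared with the subject | No. It is optional and directed to the subject |
| 9.2.2 | PI or Co-Investigator judgement on expected adverse events | No. It does not cover screening answers as such |
| 15.1 | Investigator supervision, study-team review of source documents, and investigator or designee review of adverse events and unanticipated problems | No. No timing is given, and questionnaire answers are not among the items reserved for that review |
| Appendix A, Eligibility Assessment footnote | Scheduling and subject instructions | No |

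Several of these allow an investigator to learn of the answer and act on it. None requires that this happen before eligibility is settled.

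**Is there time for such a step?** Yes. The form is graded when completed. Appendix A marks randomization under Screening or PET/MRI #1, and its footnote places it after eligibility and before Day 0.

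**The case against.** The best reply is that the protocol already covers such a person by other means. The general risk criterion is mandatory once met, and its list is introduced as examples, so a psychiatric risk is not outside it. Staff must look at item 9 in order to hand out the flyer. The history and physical exam are part of the same screening. Section 5.5 lets an investigator stop participation for any condition or situation that makes continuing against the subject's interest, and separately where "The subject meets an exclusion criterion (either newly developed or not previously recognized) that precludes further study participation". Naming no decision-maker in 5.3 is a general drafting habit and not particular to item 9.

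Later safeguards exist too:

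- Section 8.1.4 has mood questionnaires before and after each stimulation session.
- Appendix A collects PANAS and adverse events from Screening onward.
- The side-effects form lists acute mood change.
- Section 2.3.1 puts a physician at hand for PET, and 6.2 has one on pager for stimulation sessions.
- Volunteers receive telephone numbers for the PI and the coordinator.

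A suicidal statement might also be recorded as an adverse event and so reach the investigator or designee under 15.1. Finally, the Manual of Procedures may contain an escalation step.

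Most of this stands, and it rules out three stronger readings that a reader might infer:

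- **That the protocol allows such a person to be enrolled regardless.** It does not: a judgement of increased risk requires exclusion.
- **That a flyer is all the attention a participant would receive during the study.** The safeguards above show otherwise.
- **That the study has no escalation procedure.** The documents cannot show this, because the Manual of Procedures is a separate document.

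What the reply does not supply is the missing link. The risk criterion works only if someone with authority connects the answer to it. Later mood and adverse-event collection comes after the eligibility decision or has no stated timing, and the schedule does not ask item 9 again.

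**Conclusion.** The point holds for the protocol text. For an item 9 answer of 2 or 3, the only prescribed response is a flyer. The score exclusion can be passed with up to 17 or 16 points on the other items, and no stated step ensures that an investigator considers the answer before eligibility is decided.

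The documents give no frequency for these answers, alone or combined with a total of 19 or less. The number affected is therefore unknown; it is probably small. No endpoint, sample size or analysis is affected.

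The conclusion assumes that no step outside the protocol closes the gap. If the Manual of Procedures already contains one, only a cross-reference is needed. Otherwise the change should be made: the event is rare but potentially grave, and the remedy is cheap.

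**What to change.** Amend the 5.2 footnote so that staff report any item 9 answer of 2 or 3, at any total score, to the PI or a Co-Investigator, in person or by telephone, at the Screening visit and before eligibility sign-off or randomization. Document the investigator's eligibility and care decision on the screening CRF. Keep the flyer, and leave the clinical response to the study clinicians. If the Manual of Procedures already has this step, cite it in the footnote.

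The cost is one or two sentences, one CRF line and the IRB approval that 14.2 requires for any amendment. An investigator must be reachable during Screening visits, which the protocol does not now state, and there may be an occasional extra screen failure. Because the report comes before assignment, the masking of the PI and Co-Investigator in 5.4.2 is not affected.

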5.3. STRATEGIES FOR RECRUITMENT AND RETENTION

We will recruit 60 episodic migraine patients divided into 2 groups: 30 for the active M1 HD-tDCS group and 30 for the placebo HD-tDCS group. In addition, we will use the data from up to 10 healthy controls who were recruited and scanned during the NINDS-K23062946 project (IRBMED #HUM00027383; [name], Principal Investigator). We will then recruit healthy volunteers to a total of 30 age- and gender-matched healthy subjects.

Recruited patients will be screened from the UMClinicalStudies.org (formerly Engage) recruitment network and the University of Michigan. In addition to active referral from pain centers, advertisements will be placed in other pain clinics in the region. In-hospital advertisements will also be placed in pain clinics and departments at the institution, as well as across the university.

Subjects recruited will be prescreened by phone using an initial IRB-approved questionnaire. Those who pass the phone screening will be scheduled for an in-person Screening Visit, which will commence with a verbal and written informed consent process. Once informed consent has been obtained, subjects will undergo further screening by obtaining a history and performing a physical exam and QST. Those subjects who are determined to be eligible to enter the study will be enrolled into either the migraine or healthy volunteer pools; if migraine, they will be randomized to active or sham treatment.

Study duration per subject is expected to be less than 3 months; however due to the scheduling of PET and MRI visits, visit reminders (eg, phone and/or email; subject preference) may be implemented to help with retention.

During the course of participation, subjects will be compensated according to amounts stated in the informed consent form and approved by the IRB.

5.4. TREATMENT ASSIGNMENT PROCEDURES

5.4.1. RANDOMIZATION PROCEDURES

Participants initially will be screened by phone. After clinical exam and diagnosis of episodic migraine (confirmed by IHS/ICHD-3-beta criteria) participants will be randomized to the treatment HD-tDCS or sham groups using the Taves covariate adaptive randomization method. Using this method, a new participant will be sequentially assigned to a group based upon the previous assignments of other participants and certain covariates. The first eight migraine participants will be randomized by coin flip and the remaining migraine participants will be randomized by age and gender, following the Taves covariate adaptive randomization protocol. Healthy volunteers will be age- and gender-matched to the earlier enrolled participants.

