migraine patients are associated with μOR BP_{ND} in the thalamus and other pain-related regions, even during interictal phase

(non-headache phase).

To determine whether 10 daily sessions of M1 HD-tDCS have modulatory effect on clinical and experimental pain measures in

migraine patients.

To investigate whether repetitive active M1 modulation induces/reverts thalamic µOR BP_{ND}, and whether those changes are associated with clinical and experimental pain

measures in migraine patients.

Population: 60 Patients age 18-65 years (inclusive) with episodic migraine

(ICHD-3-beta); AND

30 age and gender matched healthy subjects

Subjects will be recruited from the UMClinicalStudies.org database, the clinics at the University of Michigan (UM), and

from other clinics in the region

Phase: 2

Number of Sites: 1

Study Duration: 5 YRS

Investigation and Modulation of the Mu-Opioid Mechanisms in Migraine (In Vivo) Protocol HUM00107286 Version 0.6 12 December 2018

Subject Participation

Approximately 3 Months

Duration:

Description of Agent High-de

or Intervention:

High-definition transcranial direct current stimulation (HD-

tDCS)

Estimated Time to

4 Years

Complete Enrollment:

Schematic of Study Design I:

Screening Period	Week before daily M1 HD-tDCS sessions (Neuromodulation)	Active / Sham Neuromodulation (10 Daily Sessions) M-F x2		Week after daily M1 HD-tDCS sessions	Follow-up Period ⇒
First Appt	PET/MRI Sessions	5 Daily Sessions	5 Daily Sessions	PET/MRI Sessions	Follow-up at 1 Week and at 1 Month and 2 Months Following Neuromodulation

.....

Schematic of Study Design II:

Timing (Relative to Day 0)	Procedure		
PreScreening (Up to 8 weeks prior to Day 0)	Phone Call: IRB-Approved Prescreening Checklist/Script		
Screening (Up to 3 weeks prior to Day 0)	Informed Consent Demographics History and Physical Exam Questionnaires Randomization, once subjects have been consented		
PET and MRI #1 (Up to 1 week prior to Day 0)	QST PET #1 Workup Questionnaires (PET-specific) Pregnancy Test and Drug Screen CFN (11C-carfentanil) Injection MRI #1 Screening Form (MRI-specific) MRI Questionnaires*		
HD-tDCS x 10 Daily Sessions (Day 0 - 11; Week 1 and 2)	Migraine Active Questionnaires ≤2 mA current for 20 min/day x 10 days (M-F over 2 wks)	Migraine Sham Control Questionnaires ≤2 mA current for 30 sec at start plus 30 sec at end of session x 10 days (M-F over 2 wks)	* Healthy volunteers complete participation after PET/MRI#1 visit

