5.4.2. MASKING PROCEDURES

The PI, Co-Investigator, and any members of the research staff who will be analyzing study data will be masked to participant treatment. The Research Coordinator and any study staff who will be involved in the treatment of the study participants on the HD-tDCS study days will be unmasked.

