APPENDIX A: SCHEDULE OF EVENTS

APPENDIX B: QUESTIONNAIRES

APPENDIX A: SCHEDULE OF EVENTS

Procedures	Phone PreScreening (Dav –56 to -22)	Screening (Day-21 to -1)	PET/MRI #1 (Day -21 to -1)	HD-tDCS #1-10 (Days 0-4 & Days 7-112)	PET/MRI #2 (Day 16 ± 2)	Follow Up Week #1 (Day 16 ± 2)	Follow Up Month #1 (Day 37 ± 2)	Follow Up Month #2 Day 65 ± 2)	Early Termination ³
Prescreening Script/Checklist	X								Ш
Informed Consent		X							
Adverse Events		X	X	Х	Х	X	Х	Х	X
Medical/Dental History and Physical		X							
Medication History/ Concomitant Medications		X	X	Х	Х	X	х	Х	
Pregnancy Test (Dipstick) and Drug Screen ⁴			PET Only		PET Only				
Quantitative Sensory Testing (QST)			Х		Х				
Eligibility Assessment ⁵		X							
RANDOMIZATION		X ⁶	X ₆						
PET			X		Х				
Sustained Thermal Pain Threshold Stress (STPTS) PET Challenge			X		х				
Blood Sampling ⁷ Single Draw, Genetics Serial Samples, Biomarkers			PET Only		PET Only				
MRI			Х		Х				\square
HD-tDCS (M-F for 2 weeks)				10X8					

² Missed days can be doubled within the (M-F) x 2 schedule and with study team approval

³ If subject completes an in-person visit

⁴ Safety screen for ¹¹C-carfentanil

⁵ Schedule subject visits and provide subject with instructions (PET & MRI)

⁶ Subjects will be randomized after they have met eligibility and have been consented. This will occur prior to Day 0 ⁷ If subject has consented to sample future use sub-study.

⁸ See Section 6 for active vs healthy volunteer treatment paradigm

Procedures	Phone PreScreening (Dav –56 to -22)	Screening (Day -21 to -1)	PET/MRI #1 (Day -21 to -1)	HD-tDCS #1-10 (Days 0-4 & Days 7-11 ²)	PET/MRI #2 (Day 16 ± 2)	Follow Up Week #1 (Day 16 ± 2)	Follow Up Month #1 (Day 37 ± 2)	Follow Up Month #2 Day 65 ± 2)	Early Termination ³
Questionnaires									
Demographics		X ₉							
MIDAS Questionnaire		X ₉							
Beck Depression Inventory		X ₈							
"Expectation of Effect"		X							
McGill Pain Questionnaire (Long Form)		X							
McGill PQ (Short Form)		X	X	X	Х	Х	X	Х	
PANAS ⁹		X ₉	X ₉	X	Х	Х	X	Х	
GeoPain (via iPad)8		X	X	X	Х	Х	Х	Х	
Visual Analog Pain Scale ⁸		Х	X	X	Х	Х	Х	Х	\Box
Allodynia Questionnaire		Х	Х		Х	Х	Х	Х	\square
PET Subject Information Sheet			X ₉		Х				┌┤
Pittsburgh Sleep Quality Index		X ⁹				Х	Х	Х	
tDCS AE Questionnaire				X	Х	Х	Х	Х	┌┤
H.O.P.E. Questionnaire						X	X	Х	

⁹ At Screening, Before and After MRI/PET Scans and tDCS Sessions, and at Follow Up Visits

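### After eight coin flips the allocation rule has no described random element, and the schedule lets randomisation precede baseline tests and eligibility screens

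*Combined protocol and SAP*

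**What the plan says.** **Allocation.** Section 5.4.1 uses a coin flip for the first eight migraine patients. For the rest, "the remaining migraine participants will be randomized by age and gender, following the Taves covariate adaptive randomization protocol", and under that method "a new participant will be sequentially assigned to a group based upon the previous assignments of other participants and certain covariates". The section gives no assignment probability, tie rule, age categories, concealment step or operator.

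**Who knows the arms.** Section 5.4.2 masks the PI, the Co-Investigator and the staff who analyse data. It unmasks "The Research Coordinator and any study staff who will be involved in the treatment of the study participants" on HD-tDCS days. The trial has one site.

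**Timing.** Section 5.3 puts eligibility first: "Those subjects who are determined to be eligible to enter the study will be enrolled into either the migraine or healthy volunteer pools", with migraine patients then randomised. Appendix A footnote 6 agrees: "Subjects will be randomized after they have met eligibility and have been consented". However, Schematic of Study Design II lists "Randomization, once subjects have been consented" in its Screening row. The Appendix A grid ticks randomisation under both Screening and PET/MRI #1, and section 7.3 asks only that it follow consent and precede Day 0.

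**The concern.** Covariate-adaptive allocation protects against selection only if the next assignment cannot be foreseen. Here the inputs to the next assignment are past arms, age and gender, and the unmasked staff know the past arms. If those staff also take part in screening or scheduling, they could influence who is enrolled and when, according to the arm that is coming.

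Timing adds two exposures if randomisation takes place at Screening:

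- Baseline algometry could be done with the arm known. Section 8.1.1 describes the thermal test as subject-controlled but does not say this of algometry.
- A patient who then fails a PET-day or MRI screen is lost after randomisation.

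What is at stake is the active-versus-sham comparison in Aim 2 and any sham comparison in Aim 3. The listed primary outcome (migraine against healthy controls, section 3.3) and the pre/post-active analysis in Aim 3 (section 11.1) do not depend on allocation.

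**Working it through.** **Predictability.** The documents give no figure to reproduce, so the rule was simulated.

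*Inputs from the protocol:* 60 patients allocated 1:1 (section 4); eight coin flips, then allocation by age and gender (section 5.4.1); women to men 3:1 (section 14.4). The rule governs 60 − 8 = 52 patients.

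*Assumptions:* 2, 3 or 4 equal-sized age bands; equal weights; the patient goes to the arm with the smaller sum of existing counts for that patient's sex and age band; ties broken by a fair coin. There were 2,000 simulated trials per setting.

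1. The share of assignments 9–60 fully forced is 0.743 / 0.736 / 0.732 for 2 / 3 / 4 bands. Ties make up the remaining 0.257 / 0.264 / 0.268.
2. A fully informed observer is right on every forced assignment and on half the ties. For two bands this is 0.743 + 0.257/2 = 0.872; for three, 0.736 + 0.264/2 = 0.868. Expected correct guesses: 0.868 × 52 = 45.1, against 0.5 × 52 = 26.
3. If the balancing arm is instead assigned with probability 0.8, about 0.814 of assignments have a preferred arm with two bands. The rate becomes 0.814 × 0.8 + 0.186 × 0.5 = 0.744.

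Share of guesses correct, by what the observer uses:

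| Observer | Deterministic | Probability 0.8 |
|---|---|---|
| All arms by age band and sex | 87% | 74% |
| Tally of arms within sex | 73–74% | 65–66% |
| Smaller arm so far | 69–72% | 62–64% |
| Opposite of last arm | 62–67% | 55–57% |
| Full tally, last patient's arm unknown | 63–70% | 65–68% |
| As above, also inferring the unknown arm | about 80% | about 70% |

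With 50% women, the forced share and the fully informed rate are essentially unchanged (73–74% and 86–87%).

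**Balance cost of 0.8.** The mean final arm-size difference rises from about 0.3–0.5 to 1.0–1.2 patients, with a 95th percentile of up to 4. Section 11.2 plans on 24 completers per group. A two-sample t-test has noncentrality d × √(n₁n₂/(n₁+n₂)), and d = 0.83 is the effect that 24 per group detects with about 80% power. (Section 11.2 states 1.2, at which power would be about 98%.)

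- 24 vs 24: 0.83 × √12 = 2.88, power 80.4%.
- 26 vs 22: 0.83 × √(572/48) = 2.87, power 80.1%.

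**Timing, passages side by side.**

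- *Permits randomisation at Screening:* the Schematic II Screening row, the first Appendix A tick, and section 7.3.
- *Scheduled later, at PET/MRI #1:* QST, PET, MRI, pregnancy test and drug screen (Schematic II and Appendix A), and the MRI screening form (Schematic II).
- *Exclusion criteria:* pregnancy and failure of the MRI or PET Center safety checklist (section 5.2).

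On this schedule, some checks bearing on exclusion come after the earliest permitted randomisation. That does not fit the eligibility-first rule in section 5.3 and footnote 6.

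**The case against.** **Silence is not determinism.** Section 5.4.1 calls the procedure randomised and names a method. A tie rule or concealment step may sit in the Manual of Procedures, which was not among the documents reviewed. That is fair. However, the Supplemental Materials page says the manual is not part of the protocol and can change without amendment, so the safeguard belongs in section 5.4.1.

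**No passage says unmasked staff enrol patients.** This stands: opportunity is not misconduct. Equally, no passage separates them from screening, and section 6.4 has study staff taking part in scheduling.

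**The 87% is idealised.** This stands. It assumes every earlier arm is known at once, whereas treating staff may learn an arm only from Day 0. With one patient's arm still unknown, a plain tally does 63–70%, and the 0.8 rule barely changes that (65–68%). An observer who infers the missing arm still reaches about 80%, falling to about 70%.

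**The timing problem may be drafting only.** Section 2.3.1 has MR risks excluded by history before inclusion, section 5.2 wants a negative pregnancy test before any procedure, section 5.3 places QST in screening, and Appendix A ticks the eligibility assessment at Screening. The PET-day dipstick and MRI form recur at the second scan, so they may be rechecks. These passages soften the point, but they conflict with the schematic and grid and do not withdraw the permission to randomise early.

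**The algometry harm is conditional.** No passage says who performs QST or that the tester knows the arm. This also stands.

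**Conclusion.** The concern holds as a matter that should be corrected, with medium confidence. As written, 52 of 60 assignments follow a rule with no described random element. Under the assumed age bands, equal weights and random ties, about three in four of them are forced. The range from 62–67% for the crudest guess to 87% with full tracking compares with 50% for unpredictable allocation.

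A correct guess is not itself bias, and the documents do not allow any resulting bias to be sized. No screen-failure rate is given, so loss after early randomisation cannot be sized either. Early randomisation is permitted, not required. The exposure is confined to the sham-controlled comparisons.

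**What to change.** 1. In section 5.4.1, state that after the first eight patients the imbalance-minimising arm is assigned with a stated probability below 1 (for example 0.8), and that ties are broken at random.
2. In Schematic II, section 7.3 and Appendix A, place randomisation only after PET/MRI #1, baseline QST and the PET/MRI screens, and before Day 0. Delete the Screening tick. Section 7.3 and the second Appendix A tick already permit this slot.
3. Separately, reconcile the passages on which visit includes QST (section 5.3 against Schematic II and Appendix A) and on when the pregnancy test is done (section 5.2 against Appendix A).

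The cost is protocol wording and the IRB approval that section 14.2 requires for any amendment, with no added visits or staff. The loss of balance is negligible: even 26 vs 22 completers lowers power only from 80.4% to 80.1%.

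Two limits remain. Some predictability persists because treating staff learn each arm from Day 0, and neither change protects the QST repeated at PET/MRI #2.
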